4.1 Rationale for study design

The design of this study addresses the primary objective of assessing the effect of LNP023 on PNH associated hemolysis and takes into account the rarity of this disease and the objective nature of the measurement.

The main key study design elements are described below:

Commercially Confidential Information

- This is a non-placebo-controlled study since the absence of a placebo response for LDH in this patient population has been demonstrated ([Hillmen et al 2006](#)), and is expected given the nature of the primary outcome measure (LDH). In addition, when considering available treatment options, restricting PNH patients to placebo treatment may be considered unethical.

Commercially Confidential Information

- Treatment extension of approximately 2 years for patients responding to LNP023 treatment was included to assure treatment of the patients who otherwise have limited treatment options
- The taper down period of 2 weeks was included to mitigate potential risk of increased hemolysis after LNP023 discontinuation

Commercially Confidential Information

- Treatment comparisons within patient are included with the advantage that within patient variation is assumed to be less than between patients

Commercially Confidential Information

4.2 Rationale for dose/regimen and duration of treatment

4.2.1 Dose regimen and dose span

Commercially Confidential Information

4.2.2 Minimal treatment duration of each dose

Commercially Confidential Information

4.3 Rationale for choice of control drugs (comparator/placebo) or combination drugs

Not applicable

4.4 Purpose and timing of interim analyses/design adaptations

Commercially Confidential Information

Commercially Confidential Information

4.5 Risks and benefits

The risk to subjects in this trial will be minimized by adherence to the eligibility criteria, close clinical monitoring, early stopping rules, periodic review of the safety data, and guidance for the investigators in the Investigator's Brochure. The most relevant risks are described below. A complete list of toxicological findings is available in the Investigator's Brochure. Women of child bearing potential (WOCBP) must be informed that taking the study treatment may involve unknown risks to the fetus if pregnancy were to occur during the study, and agree that in order to participate in the study they must adhere to the highly effective contraception requirements outlined in the [Section 5.2 \(Exclusion Criteria\)](#).

Commercially Confidential Information

Commercially Confidential Information

4.5.1 Blood sample volume

Less than 500 mL of blood is planned to be collected from each study patient during 19 weeks of Period 1 and Period 2 of the study. Up to approximately 450 mL is planned to be collected from each study patient during approximately 2 years of Extension Period 3. Total maximum blood volume collected during the study will not exceed 950 mL.

Additional samples may be required for safety monitoring. Timings of blood sample collection are outlined in the [Assessment schedule](#). A summary blood log is provided in the Site Operations Manual (SOM). Instructions for all sample collection, processing, storage and shipment information are available in laboratory manual.

See the section on the potential use of residual samples.

4.5.2 Rationale for Public Health Emergency mitigation procedures

During a Public Health emergency as declared by Local or Regional authorities i.e. pandemic, epidemic or natural disaster, mitigation procedures to ensure participant safety and trial integrity are listed in relevant sections. Notification of the Public health emergency should be discussed with Novartis prior to implementation of mitigation procedures, and permitted/approved by Local or Regional Health Authorities and Ethics Committees as appropriate.

5 Population

Ten adult, male and female PNH patients with active hemolysis, are planned to complete the study. Additional patients might be enrolled to replace patients who discontinue the study or treatment for reasons other than safety or lack of efficacy.

The investigator must ensure that all patients being considered for the study meet the following eligibility criteria. No additional criteria should be applied by the investigator, in order that the study population will be representative of all eligible patients.

Patient selection is to be established by checking through all eligibility criteria at screening and/or baseline as specified below. A relevant record (e.g., checklist) of the eligibility criteria must be stored with the source documentation at the study site.

Deviation from **any** entry criterion excludes a subject from enrollment into the study.

5.1 Inclusion criteria

Subjects eligible for inclusion in this study must meet **all** of the following criteria:

1. Written informed consent must be obtained before any assessment is performed.
2. Male and female patients at least 18 years old at baseline.
3. Diagnosis of active PNH based on documented clone size of $\geq 10\%$ by RBCs and/or granulocytes, measured by GPI-deficiency on flow cytometry (screening or medical history data acceptable).

4. LDH values $\geq 1.5 \times$ upper limit of the normal range (ULN) for at least 3 measurements over a maximum of 8 weeks prior to Day 1 (Screening, baseline or medical history data acceptable).
5. Hemoglobin level $< 10.5 \text{ g/dL}$ at Baseline.
6. For Period 3 of the study, patients who as per judgment of Investigator benefit from LNP023 treatment based on reduced hemolytic parameters as compared to Screening and Baseline.
7. Vaccinations against *N. meningitidis*, *S. pneumoniae* and *H. influenzae* is required at least 4 weeks prior to first dosing with LNP023 (existing vaccinations should provide effective titers at time of LNP023 treatment start). If LNP023 treatment has to start earlier than 4 weeks post vaccination, prophylactic antibiotic treatment must be initiated.
8. Able to communicate well with the investigator, to understand and comply with the requirements of the study.

5.2 Exclusion criteria

Subjects meeting any of the following criteria are not eligible for inclusion in this study:

1. Participation in any other investigational drug trial or use of other investigational drugs at the time of enrollment, or within 5 elimination half-lives of enrollment, or within 30 days, whichever is longer; or longer if required by local regulations.
2. Patients treated with eculizumab or any other complement inhibitor less than 3 months prior to study Day 1
3. Known or suspected hereditary or acquired complement deficiency.
4. History of currently active primary or secondary immunodeficiency.
5. History of splenectomy.
6. History of bone marrow/ hematopoietic stem cell or solid organ transplants (e.g. heart, lung, kidney, liver).
7. Evidence of malignant disease, or malignancies diagnosed within the previous 5 years.
8. Patients with laboratory evidence of bone marrow failure (reticulocytes $< 60 \times 10^9/\text{L}$, or platelets $< 50 \times 10^9/\text{L}$, or neutrophils $< 1 \times 10^9/\text{L}$) verified both at screening and baseline.
9. History of recurrent meningitis, history of meningococcal infections despite vaccination, as verified at both screening and baseline.
10. Presence or suspicion (based on judgment of the investigator) of active infection within 2 weeks prior to first dose of LNP023, or history of severe recurrent bacterial infections.
11. A positive HIV, Hepatitis B (HBV) or Hepatitis C (HCV) test result at screening.
12. Patients on immunosuppressive agents such, as but not limited to, cyclosporine, tacrolimus, mycophenolate or mycophenolic acid, cyclophosphamide, methotrexate or IV immunoglobulins, less than 8 weeks prior to first treatment with LNP023, unless on a stable regimen for at least 3 months prior to first LNP023 dose.
13. Systemic corticosteroids unless on a stable dose for at least 4 weeks before randomization.
14. Severe concurrent co-morbidities not amenable to active treatment; e.g., patients with severe kidney disease (CKD stage 4, dialysis), advanced cardiac disease (NYHA class IV), severe pulmonary arterial hypertension (WHO class IV), or unstable thrombotic

event, as judged by the investigator, both at screening and baseline (unless baseline was skipped).

15. Any medical condition deemed likely to interfere with the patient's participation in the study, or likely to cause serious adverse events during the study.
16. History of hypersensitivity to the study treatment or its excipients or to drugs of similar chemical classes.
17. Female patients who are pregnant or breastfeeding, or intending to conceive during the course of the study.
18. Women of child-bearing potential, defined as all women physiologically capable of becoming pregnant, unless they are using highly effective methods of contraception during dosing and for 1 week after stopping of investigational drug.

Highly effective contraception methods include:

- Total abstinence from heterosexual intercourse (when this is in line with the preferred and usual lifestyle of the subject). Periodic abstinence (e.g., calendar, ovulation, symptothermal, post-ovulation methods) and withdrawal are not acceptable methods of contraception.
- Female sterilization (have had surgical bilateral oophorectomy with or without hysterectomy), total hysterectomy or tubal ligation at least six weeks before taking investigational drug. In case of oophorectomy alone, only when the reproductive status of the woman has been confirmed by follow up hormone level assessment.
- Male sterilization (at least 6 months prior to Screening). For female subjects on the study the vasectomized male partner should be the sole partner for that subject.
- Use or oral (estrogen and progesterone), injected or implanted hormonal methods of contraception or placement of an intrauterine device (IUD) or intrauterine system (IUS) or other forms of hormonal contraception that have comparable efficacy (failure rate below 1%), for example hormone vaginal ring or transdermal hormone contraception.

In case of use of oral contraception, women should be stable on the same pill for a minimum of 3 months before taking the investigational drug.

If local regulations deviate from the contraception methods listed above and require more extensive measures to prevent pregnancy, local regulations apply and will be described in the Informed Consent Form (ICF).

Women are considered post-menopausal and not of child bearing potential if they have had 12 months of natural (spontaneous) amenorrhea with an appropriate clinical profile (e.g. age appropriate, history of vasomotor symptoms) or have had surgical bilateral oophorectomy (with or without hysterectomy), total hysterectomy or tubal ligation at least six weeks ago. In the case of oophorectomy alone, only when the reproductive status of the woman has been confirmed by follow up hormone level assessment is she considered not of child bearing potential. Refer to [Section 8.4.4](#) (Pregnancy and Assessments of Fertility).

No additional exclusions may be applied by the investigator, in order to ensure that the study population will be representative of all eligible subjects

6 Treatment

6.1 Study treatment

Patients will receive study medication at study center for days when visits are planned and at home during remaining study days. Details on the requirements for storage and management of study treatment, and instructions to be followed for subject numbering, prescribing/dispensing and taking study treatment are outlined in the SOM.

As per [Section 4.5.2](#), during a Public Health emergency as declared by Local or Regional authorities i.e. pandemic, epidemic or natural disaster, that limits or prevents on-site study visits, delivery of IMP directly to a participant's home may be permitted (if allowed by Local or Regional Health Authorities and Ethics Committees as appropriate) in the event the Investigator has decided that an on-site visit by the participant is no longer appropriate or possible, and that it is in the interest of the participant's health to administer the study treatment even without performing an on-site visit. The dispatch of IMP from the site to the participant's home remains under the accountability of the Investigator. In this case, regular phone calls or virtual contacts (frequency as per planned visit) will occur between the site and the participant for instructional purposes, safety monitoring, and investigation of any adverse events, ensuring participants continue to benefit from treatment, and discussion of the participant's health status until the participants can resume visits at the study site.

6.1.1 Investigational and control drugs

Table 6-1 Investigational and control drug

| Investigational/ Drug | Pharmaceutical Dosage Form | Route of Administration | Design | Sponsor (global or local) |
|---------------------------------------|-------------------------------|----------------------------|--------|------------------------------|
| Commercially Confidential Information | | | | |

6.1.2 Additional study treatments

No additional treatment beyond investigational drug are included in this trial.

6.1.3 Treatment arms/group

Subjects will be randomized at baseline to sequence 1 or sequence 2.

Commercially Confidential Information

Commercially Confidential Information

6.2 Other treatment(s)

6.2.1 Concomitant therapy

The investigator must instruct the subject to notify the study site about any new medications he/she takes after the subject was enrolled into the study.

All medications, procedures and significant non-drug therapies (including physical therapy and blood transfusions) administered after the subject was enrolled into the study must be recorded in the specific case report form (CRF) page.

Medication entries should be specific to trade name, the single dose and unit, the frequency and route of administration, the start and discontinuation date and the reason for therapy.

Each concomitant drug must be individually assessed against all exclusion criteria/prohibited medication. If in doubt, the investigator should contact the Sponsor medical monitor before enrolling a patient or allowing a new medication to be started. If the patient is already enrolled, contact the Sponsor to determine if the patient should continue participation in the study.

6.2.1.1 Vaccinations

All patients need to complete vaccinations against *N. meningitidis*, *S. pneumoniae* and *H. influenzae* at least 4 weeks prior to starting LNP023 treatment. Vaccinations will be performed according to local recommendations for patients with complement deficiencies, if prior vaccination cannot be confirmed. The choice of vaccine(s) should take into account the serotypes prevalent in the geographic areas in which study patients will be enrolled.

After initial immunization, booster doses of the vaccinations should be administered according to the label of the vaccination used. The screening period may be extended to allow vaccination procedures to be completed. This is applicable for vaccinations only and all the other screening assessments should be performed within the period described in the [Assessment Schedule](#).

6.2.1.2 Prophylactic antibiotics

In case LNP023 treatment has to start earlier than 4 weeks post-vaccination, prophylactic antibiotic treatment must be initiated. In addition, to reduce risk of infection, antibiotics will be required for patients with any sign of infection (see [Section 6.6.2](#)).

6.2.1.3 Permitted concomitant therapy requiring caution and/or action

LNP023 has been shown to have a weak inhibition potential for the liver uptake transporter OATP1B1 and respective calculations revealed that the exposure (AUC) of sensitive substrates may be increased by about 1.25 fold. It is therefore recommended to use respective co-medications with a narrow therapeutic index with caution.

As LNP023 is also an OATP1B1/3 substrate, co-administration with strong inhibitors may potentially lead to minor exposure increase (<1.5 fold) for LNP023.

6.2.2 Prohibited medication

Use of the medications displayed in the table below is NOT allowed.

Commercially Confidential Information

The investigator should consult with Novartis medical expert prior treating a patient with this type of co-medication.

Table 6-2 Prohibited medication

| Medication | Prohibited period | Action to be taken |
|---------------------------------------|-------------------|--------------------|
| Commercially Confidential Information | | |

6.2.3 Rescue medication

If required as per judgment of the Investigator, another medication targeting underlying pathophysiology of the disease might be used as a rescue medication. Please refer to [Section 6.6.2](#) for recommended handling of adverse events (AE).

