|--------------------------|--|
| Other assessments | Commercially Confidential Information |
| Data analysis | 
The primary efficacy variable for assessing the effect of LNP023 is response rate; where a patient will be considered a responder if LDH is below ULN or the percentage reduction from baseline in serum LDH is at least 60% at any time up to and including week 12 for that patient. In a proof of concept paradigm, a positive sign of efficacy is when the estimated response rate is at least 50%. For example, this criterion will be met when 5 out of 10 patients are considered responders.
 
Commercially Confidential Information
 |
| | 
The same mixed modelling approach will be used for other continuous response variables. Skewed data will be transformed in order to meet underlying normality and homoscedasticity assumptions. In case early escalation gives data only to two weeks for some patients, the modelling will be adjusted to suit.
 |
| Key words | PNH, hemolysis, LDH, hemoglobin |

1 Introduction

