9.1 Discontinuation

9.1.1 Discontinuation of study treatment

Discontinuation of study treatment for a patient occurs when study treatment is stopped earlier than the protocol planned duration. If possible taper-down should be implemented for patients who discontinue study treatment. Discontinuation of study treatment can be decided by either the patient, the investigator or Sponsor. Study treatment must be discontinued under the following circumstances:

- Patient decision - patient may choose to discontinue study treatment for any reason at any time.
- The investigator believes that continuation would negatively impact the safety of the subject or the risk/benefit ratio of trial participation.
- Any protocol deviation that results in a significant risk to the patient's safety.
- Pregnancy (see [Section 5.2](#))
- Use of prohibited treatment as outlined in [Table 6-2](#).
- If a liver or renal event occurs, follow the Hepatotoxicity Clinical Safety Standard Guideline or Renal Toxicity Clinical Safety Guideline, outlined in [Appendix 1](#) and [Appendix 2](#) regarding discontinuation of study treatment.
- Increases in QTcF to >500 ms or of >60 ms over baseline should be used as thresholds for patient discontinuation.
- Unsatisfactory therapeutic effect- decision to be taken after consultation with Sponsor.

If discontinuation of study treatment occurs, investigator must determine the primary reason for the subject's premature discontinuation of study treatment and record this information on the Dosage Administration CRF.

Patients who discontinue study treatment or who decide they do not wish to participate in the study further should NOT be considered withdrawn from the study UNLESS they withdraw their consent (see [Section 9.1.2](#), Withdrawal of Informed Consent). Where possible, patients who discontinue study treatment only should continue to return for study scheduled assessments.

If any patient discontinues study or study treatment with LNP023 they should be closely monitored for signs and symptoms of hemolysis.

The parameters below are suggested to be closely monitored:

- greater than 25% absolute decrease in PNH clone size (in the absence of dilution due to transfusion) in one week or less;
- increase in LDH level;
- an hemoglobin level of < 8 g/dL or a decrease of > 4 g/dL in one week or less;
- angina pectoris;
- change in mental status;
- a 50% increase in serum creatinine level; or
- thrombosis.

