12.4 Analysis of the primary endpoint(s)

12.4.1 Definition of primary endpoint(s)

The primary efficacy endpoint for assessing the effect of LNP023 is response rate, where a patient will be considered a responder if LDH is below ULN or the percentage reduction from baseline in serum LDH is at least 60% at any time up to and including Week 12 for that patient, whether or not

Commercially Confidential Information

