#### 7.1.1 Variables

The primary variable is treatment response. A responder is defined as a patient with at least 60% reduction in LDH compared to baseline or LDH below upper limit of normal (ULN) at any time up to and including Week 12 for that patient, whether or not CCI , and a non-responder anyone who doesn't meet either of these criteria.

Baseline LDH will be calculated as the average of the last three screening values prior to randomization.

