#### 7.1.2.1 Handling of missing values/censoring/discontinuations

For calculation of the success rate for the primary endpoint all patients enrolled in the study apart from those who were replaced for reasons other than safety or efficacy will be included in the denominator.

Commercially Confidential Information

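### No readable analysis rule excludes LDH measured after permitted rescue with another disease-targeting drug, so an LDH fall caused by rescue up to Week 12 could be credited to LNP023.

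*Protocol*

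**What the plan says.** **Rescue.** Protocol 6.2.3 permits, if the investigator judges it necessary, that "another medication targeting underlying pathophysiology of the disease might be used as a rescue medication". The readable text sets no time limit and does not require LNP023 to be stopped first.

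**Response.** The criterion is LDH below ULN or at least a 60% fall from baseline. Protocol 12.4.1 applies it "at any time up to and including Week 12 for that patient, whether or not", where the sentence runs into a redaction. SAP 7.1.1 has the same window and a similar gap, then defines "a non-responder anyone who doesn't meet either of these criteria". The protocol summary gives the rule as a complete sentence with the same window ("at any time up to and including week 12 for that patient") and no restriction.

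**Treatment wording.** Table 2-1 and SAP 1.3.1 word the endpoint as covering up to 12 weeks of treatment.

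**Follow-up.** Under protocol 9.1.1, where possible, "patients who discontinue study treatment only should continue to return for study scheduled assessments". Table 8-1 schedules clinical chemistry, which includes LDH (8.4.1.1), through Day 85.

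**Denominator.** Protocol 12.4.3 and SAP 7.1.2.1 count "all patients enrolled in the study apart from those who were replaced for reasons other than safety or efficacy". A redacted block follows in each document.

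**The concern.** The study purpose (protocol 1.2) is the effect of LNP023 without concomitant complement inhibition, and exclusion criterion 2 bars complement inhibitors in the 3 months before Day 1. No readable analysis rule carries that protection past Day 1.

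LDH is the marker that another complement-directed drug would be expected to move. Protocol 8.3.1 says that blocking complement-mediated lysis should lower it. Protocol 4.1 justifies having no placebo arm by the absence of a placebo response in LDH. That argument does not cover a second LDH-lowering drug given during the trial.

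A patient who does poorly on LNP023, is rescued, and then has one qualifying LDH value by Week 12 meets the readable definition of a responder. With about 10 patients, no control arm and a cut at 50%, a few such patients would matter.

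**Working it through.** **1. The plan's own figure.** Protocol 12.8.1 gives 80% probability of at least 5 responders out of 10 at a true rate of 58%. The exact binomial tail is P(X ≥ 5 | n = 10, p = 0.58) = 0.798. The figure is reproduced and is not in dispute.

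**2. Direction.** A patient responds if any value in the window qualifies. Adding post-rescue values to the window can turn a non-responder into a responder but never the reverse. Compared with counting pre-rescue values only, the observed rate can therefore only rise.

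**3. Do other readable provisions close the gap?**
- *Treatment wording (Table 2-1, SAP 1.3.1).* This suggests on-treatment values. It would remove LDH taken after LNP023 is stopped, but not LDH taken while rescue is added to LNP023.
- *Prohibited medication (Table 6-2, redacted).* Under 9.1.1, use of a listed drug means stopping LNP023. That governs treatment; the readable part does not say which LDH values count.
- *PD analysis set (SAP 5 and 7).* Subjects with deviations that matter for PD data are excluded, but the only code shown in Table 5-1 is INCL01. Permitted rescue is not in itself a deviation.
- *Non-responder definition (SAP 7.1.1).* It turns on the two LDH criteria only.

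**4. Illustrative size.** Let p be the true response rate on LNP023 and r the share of the remaining patients who are rescued by Week 12. The documents give no value for r, so it is an assumption. Assume also that every rescued patient then qualifies, which makes the results upper bounds for a given r. The observed rate is q = p + (1 − p)r, and the chance of meeting the criterion is P(X ≥ 5 | n = 10, q). For p = 0.40 and r = 10%, q = 0.40 + 0.60 × 0.10 = 0.46.

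| True rate p | r = 0 | r = 10% | r = 20% | r = 30% |
|---|---|---|---|---|
| 0.20 | 3.3% | 11.8% (q = 0.28) | 27.1% (q = 0.36) | 47.0% (q = 0.44) |
| 0.30 | 15.0% | 29.4% (q = 0.37) | 47.0% (q = 0.44) | 64.7% (q = 0.51) |
| 0.40 | 36.7% | 52.2% (q = 0.46) | 67.1% (q = 0.52) | 79.8% (q = 0.58) |

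In the last cell a drug with a true rate of 40% would look like the 58% assumed in the sample size section. The r = 0 column is what applies if nobody is rescued before Week 12, or if post-rescue values are excluded.

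**The case against.** The strongest reply is that the places where a rescue rule would sit are blacked out: the words after the response window in 12.4.1 and SAP 7.1.1, the rest of 12.4.3 and SAP 7.1.2.1, and the whole of Table 6-2. This stands. A reader might infer that the plan does convert treatment failures into responders; the documents support only that no readable rule prevents it.

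Second, a reader might infer that LDH taken after stopping LNP023 plainly counts, since such patients keep attending. The treatment wording in Table 2-1 and SAP 1.3.1 weakens that inference. It leaves rescue added to LNP023 unaddressed.

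Third, rescue before Week 12 may be rare. The plan provides for early escalation (protocol 12 and 12.5), and Table 8-1 has an extra Day 16 visit for patients without a 40% LDH reduction at Day 15. Protocol 1.1 notes that eculizumab is not available everywhere, and rescue need not be complement-directed. Failure, rescue and LDH response must all fall by Day 85. This stands as a limit on size, not on direction.

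Fourth, it is tempting to treat one or two rescued failures as given and lower the bar from 5 to 4 or 3. At p = 0.40 that yields P(X ≥ 4) = 62% and P(X ≥ 3) = 83%. The arithmetic is right, but it supposes that such patients occur and qualify in every trial, which nothing in the documents supports.

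Finally, the trial is non-confirmatory and has no formal test of the primary endpoint. That lowers the stakes, but the 50% criterion is still its declared sign of efficacy.

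**Conclusion.** The point holds on the readable text: one qualifying LDH value up to Week 12 is enough, disease-targeting rescue is allowed, and no visible rule separates the two. Any resulting bias favours meeting the 50% criterion.

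Its size cannot be estimated from the documents. At a true rate of 40%, the chance of at least 5 of 10 would move from 37% to at most 52% or 67% if 10% or 20% of non-responders were rescued and all then qualified. It would not move at all without rescue before Week 12. The conclusion also depends on the redacted text containing no limit; if it contains one, no change is needed. The stated 80% is unaffected.

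**What to change.** First check the redacted parts of protocol 12.4.1, 12.4.3 and Table 6-2, and of SAP 7.1.1 and 7.1.2.1. If they already say how LDH after rescue is treated, stop there.

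Otherwise add to protocol 12.4.1 and SAP 7.1.1: *LDH values taken after the start of rescue medication directed at the disease pathophysiology (for example another complement inhibitor) do not count toward response. A patient who starts such rescue before meeting the criterion is a non-responder.*

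Leave the denominator exception in 12.4.3 and SAP 7.1.2.1 as it is. A broader rule, making everyone who stops LNP023 a non-responder kept in the denominator, would conflict with that exception and with the replacement policy in 9.1.1.1. Add a listing of rescued patients with the dates of first response and of rescue.

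**Cost.** A short addition to each document and one listing. No new data are needed, because protocol 6.2.1 already has concomitant medication start dates recorded. The clinical rescue provision does not change. The downside is that the observed response rate may be lower if rescue occurs, including for a patient who might have responded later on LNP023 alone.
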